	• "EuroSCORE II" and corresponding footnote (footnote 't') was added to the SoA: Impaired prognosis defined as EuroSCORE II > 7% perioperative mortality at screening is exclusionary.	• Included guidance regarding EuroSCORE II in the SoA for consistency
	• A new footnote 'u' was added to "Serum sampling for immunogenicity assessment": Serum collection should be conducted where feasible. If the participant cannot attend the study visit and/or an in-home assessment is not feasible, then the serum collection can be omitted, after sponsor approval.	• To provide guidance regarding feasibility of study assessments being conducted

Section No. and Name	Description of Change	Brief Rationale
	
 
Former footnotes h and n were deleted:
 
th AF symptom diary must be used for first 30 days after surgery (or until early discontinuation if before Day 30) and during the first 7 days following Day 60, Day 90, Day 180, Day 270 and Day 360 visits. The diary should be returned to the site and be part of the medical records.
 
aDay 367 must be at least 7 days and no more than 14 days after Visit 13 (Day 360).
 
	• Additional clarification was provided in newly added footnotes
Section 2.3, Benefit/Risk Assessment	Text was revised:	
Section 3, Objectives and Endpoints; Section 9.4.1.3, Secondary Efficacy Variables	
 
The following secondary efficacy endpoints were added:
 
Percentage of participants with at least 1 continuous AF episode ≥ 6 hours during the first 30 days post-surgery
 
Percentage of participants with at least 1 continuous AF episode ≥ 12 hours during the first 30 days post-surgery
 
	New secondary efficacy endpoints were added to include events lasting longer than 6 hours and 12 hours.
Section 3, Objectives and Endpoints; Section 8.1.4.4, Re-hospitalization and Days Spent in Hospital, Table 8-7 Section 9.4.1.4, Additional Efficacy Variables	The following additional efficacy endpoints was revised: Number of non-arrhythmia cardiovascular re-hospitalizations within 30 days post-discharge	For clarification

Section No. and Name	Description of Change	Brief Rationale

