	
 
Exclusion Criterion 2.05 was revised: Prior open-chest, sternotomy cardiac surgery
 
	
 
To clarify which prior cardiac surgeries are excluded
 

	• Exclusion Criterion 4.02 was revised: Impaired prognosis defined as EuroSCORE II > 7% perioperative mortality at screening is exclusionary .	• To clarify the timepoint of the assessment
Section 6.1, Study Interventions; Table 6-1 Treatments Administered	Text was added: Each of the 5 fat pads must be injected as part of the study procedure. However, in the event where 1 fat pad is missing or is not accessible, the injection procedure can continue and only 4 mL of interventional product or placebo shall be injected. If, upon initial evaluation (ie, if injections have not yet occurred), 3 fat pads or fewer are accessible, the injection procedure should be aborted. If any injections of study intervention have already been made when the surgeon determines they are unable to inject 4 or more fat pads, the participant should remain in the study.	To clarify the decision to proceed (or not) based on initial inspection of accessible fat pads
	Table footnote was deleted: *-Each 1 of the 5 fat pads must be injected as part of the study procedure. However, in the event where 1 fat pad is missing or is not accessible, the injection procedure can continue and only 4 mL of interventional product or placebo shall be injected. If 3 fat pads or less are accessible, the injection procedure must be aborted.	

Section No. and Name	Description of Change	Brief Rationale
Section 6.2, Preparation/Handling/ Storage/Accountability	Text was revised: All unused study intervention and used kits must should be returned to the sponsor or designee at the termination of the study. Unit counts will be performed when the study intervention is returned, and all study intervention must be accounted for. Accountability logs for destroyed materials should be maintained at the site to ensure all study intervention is accounted for. Study intervention may be destroyed on site if required by local/institutional policies after sponsor approval of destruction process and documentation.	For improved accuracy
Section 6.5.2, Permitted Interventions	Text was revised: • Dosage information including dose, route of administration , and frequency	For additional guidance

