#### AGN-151607

2.02	Botulinum toxin type A (of any serotype) use within 6 months of randomization		
2.03	Has been immunized for any botulinum toxin type A serotype as determined by participant medical history		
2.04	Preoperative need for inotropes/vasopressors or intra-aortic balloon pump		
2.05	Prior open-chest, sternotomy cardiac surgery		
2.06	History of ablation for AF		
2.07	Planned ablation procedure for AF at the time of surgery		
2.08	Emergency surgery		
3.	Prior/Concurrent Clinical Study Experience		
3.01	Current enrollment in an investigational drug or device study or participation in such a study within 30 days of entry into this study		
4.	Diagnostic Assessments		
4.01	Participants have diagnostic assessments which in the opinion of the investigator prevent participation in the study.		
4.02	Impaired prognosis defined as EuroSCORE II > 7% perioperative mortality at screening is exclusionary.		
5.	Other		
5.01	Females who are pregnant, nursing, or planning a pregnancy during the study		
5.02	The participant has a condition or is in a situation which, in the investigator's opinion, may put the participant at significant risk, may confound the study results, or may interfere significantly with the participant's participation in the study		

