#### AGN-151607

- Inclusion criteria 4.01 and 4.02 are to minimize risk of pregnancy during the first 60 days of the study. Regarding 4.02 and female participants, the risk of pregnancy will be also minimized by the age criteria.
- Inclusion criteria 5.01 to 5.03 are to ensure protection of the study participants through the informed consent process.
- Inclusion criterion 6.01 is to ensure participants have no detected arrhythmias in the 48 hours prior to surgery that could impact study conduct.
- Inclusion criteria 6.02 and 6.03 is to ensure quality of the study data.
- Exclusion criteria 1.01 to 1.09 are necessary to prevent participants with medical conditions that could increase the risk of AEs with exposure to botulinum toxin type A preparation or have conditions that could confound the results of the study in the analysis of efficacy.
- Exclusion criterion 2.01 is necessary to avoid antiarrhythmic medications so any efficacy the study intervention may have is not reduced.
- Exclusion criteria 2.02 and 2.03 are necessary to avoid any effects of prior botulinum toxin type A or prior surgical procedures influencing the results.
- Exclusion criteria 2.04 to 2.08 are to ensure absence of prior cardiac procedures that may influence POAF and confound the study results.
- Exclusion criterion 3.01 is customary in clinical trials and is necessary to prevent interactions with other investigation products.
- Exclusion criteria 4.01 and 5.02 are necessary to ensure the protection and well-being of the study participants.
- Exclusion criterion 4.02 is to ensure that the perioperative risk of death is compatible with the intended study follow-up duration.
- Exclusion criterion 5.01 is to ensure protection of the fetus and mother during pregnancy.

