8.0 Demographics and Other Baseline Characteristics

Demographic parameters (age; age group; race; ethnicity; sex), baseline characteristics (weight; height; and body mass index, calculated as weight [kg]/(height [m])²), waist circumference (m), and other disease characteristics (type of surgery and number of grafts) will be summarized descriptively by treatment group for the safety population. Continuous variables will be summarized by number of participants and mean, SD, first quartile (Q1), median, minimum, third quartile (Q3), and maximum values. Categorical variables will be summarized by number and percentage of participants.

Medical history data will be coded using the Medical Dictionary for Regulatory Activities (MedDRA). The number and percentage of participants with medical history ongoing at screening will be summarized by system organ class, preferred term, and treatment group for the safety population. Data for medical history that is not ongoing at screening will be summarized and presented in a similar manner. An overall total will be provided for the study as well as by treatment group.

Prior medication is defined as any medication taken before the study treatment. Concomitant medication is defined as any medication taken on or after the day of study treatment.

Both prior and concomitant medications will be coded using the Anatomical-Therapeutic-Chemical classification text from World Health Organization (WHO) Drug Dictionary. The use of prior and concomitant medications will be summarized by the number and percentage of subjects in each treatment group for the safety population. If a participant took a specific medication multiple times or took multiple medications within a specific therapeutic class, that participant would be counted only once for the coded drug name or therapeutic class.

In addition to summarizing all medications as discussed above, a separate tabulation will also be provided for the following medications of interest:

- The following antiarrhythmics: quinidine, procainamide, disopyramide, mexiletine, flecainide, propafenone, amiodarone (including amiodarone hydrochloride, amiodarone hydrochloride w/ glucose and amiodarone;glucose), dronedarone, dofetilide, sotalol (including sotalol hydrochloride), and ibutilide.
- The following anticoagulants: warfarin (including warfarin sodium), dabigatran, apixaban, rivaroxaban, and edoxaban (including edoxaban tosilate).

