For each treatment group, the Kaplan-Meier (KM) survival analysis methodology will be used to estimate the median time (days) to first occurrence of AF during the first 30 days post-surgery using each of the 9 definitions of POAF stated in Section 10.0 above. Furthermore, the 25th and 75th percentiles of the time to the first occurrence of AF during the first 30 days post-surgery will also be estimated. The associated 95% CIs calculated using Greenwood's formula for the variance of the KM estimate will also be presented for each treatment group. Pairwise treatment comparisons of the KM curves will be performed primarily by using the log rank test stratified by type of surgery and age group. Time to event data will also be compared between treatment groups using Cox proportional hazards models adjusting for baseline risk factors of POAF (type of surgery, and age group), with hazard ratios and their 95% CIs presented for each pairwise comparison. Cox proportional hazards models additionally adjusting for total analyzable time during the first 30 days post-surgery will also be analyzed. The difference in restricted mean survival time between treatment groups for time to first occurrence of AF during the first 30 days post-surgery (i.e., restricted time $\tau = 30$ days) will be compared using a nonparametric K-sample chi-square test stratified by type of surgery and age group. Participants who do not experience an AF episode during the first 30 days post-surgery will be censored at the maximum timepoint during the first 30 days post-surgery for which they have recorded data.

For the time to first occurrence of AF during the first 30 days post-surgery, a supplementary analysis will be performed based on the Supplementary ePatch Analysis Sets (SEA-7 and SEA-30). The supplementary analysis will use the same methods described above.

For each minimum duration specified above for the percentage of participants with at least 1 continuous AF episode during the first 30 days post-surgery, a supplementary analysis will be performed based on the Supplementary ePatch Analysis Sets (SEA-7 and SEA-30). The supplementary analysis will use the same methods used to analyze the primary efficacy variable. For these endpoints, subgroup analyses will also be performed using the same methods described above based on the correct stratification group [type of surgery (presence or absence of valve surgery) and age group (< 65 or \geq 65 years)].

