10.3 Additional Efficacy Variables

Hospital and ICU Length of Stay

Hospital length of stay for the initial care of indication under study is defined as the time (days) from ICU admission date/time to the date/time of discharge from the hospital. ICU length of stay is defined as the time (hours) from the ICU admission date/time to the date/time of discharge from the ICU. For participants not admitted to the ICU, ICU length of stay will be set to zero and hospital length of stay will be defined as the time (days) from end date/time of study drug administration to date/time of discharge from hospital. For subjects missing ICU admission date/time, ICU admission date/time will be imputed to the end date/time of study drug administration. The date/time of death will be used to derive hospital length of stay for participants who died at the hospital (and ICU length of stay, for participants who die in the ICU).

Descriptive statistics (n, mean, SD, Q1, median, Q3, min, max) for hospital and ICU length of stay will be presented by:

- treatment group
- region (U.S. versus non-U.S.) and treatment group
- country and treatment group
- sites and treatment group

Between-group treatment comparisons in hospital and ICU length of stay will be performed for each AGN-151607 treatment arm versus placebo using the following methods:

- An ANOVA model with treatment group, type of surgery, age group, and region as factors
- An ANOVA model with treatment group and region as factors
- An ANOVA model with treatment group and country as factors

- A stratified Wilcoxon (Van Elteren) test, stratified by type of surgery, age group, and region
- A stratified Wilcoxon (Van Elteren) test, stratified by type of surgery and age group

Descriptive statistics of hospital length of stay measured from the time of initial hospital admission to discharge will be presented by:

- treatment group
- region (U.S. versus non-U.S.) and treatment group
- country and treatment group
- sites and treatment group

ANOVA models, as described above, will be used to estimate confidence intervals for difference in mean hospital length of stay measured from the time of initial hospital admission between each AGN-151607 treatment arm and placebo.

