16.0 Changes to Analyses Specified in Protocol

The following changes were made to analyses specified in the protocol:

- Logistic regression models adjusting for baseline risk factors of POAF (type of surgery, and age group) will not be performed for the primary endpoints of the proportion of participants with at least one continuous AF Episode during the first 30 days post-surgery.
 - Rationale: adjusted odds ratios, stratified by type of surgery (presence or absence of valve surgery) and age group (< 65 or ≥ 65 years), with associated 95% CIs and P-values, are already presented using the CMH test.
- In lieu of t-tests, ANOVA models will be used to analyze hospital and ICU length of stay. Stratified Wilcoxon (Van Elteren) tests will be used for supplementary analyses for these variables, regardless of skewedness.
 - Rationale: ANOVA models are commonly used for stratified analyses of continuous outcomes. The stratified Wilcoxon (Van Elteren) test may provide value as a supplementary analysis even if the distribution is not skewed.
- Percentage of participants with at least 1 continuous AF episode ≥ 6 minutes during the first 30 days post-surgery was added as a secondary efficacy variable based on input from cardiology experts.

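### EuroSCORE II is scheduled for every participant but used only as an eligibility cut-off; tabulating it, and adjusting for it and for continuous age, could add precision or power of unknown size

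*Protocol*

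**What the plan says.** - **Collection.** The Schedule of Activities (Protocol 1.3, repeated as SAP Table 4–1) has a EuroSCORE II row, marked at the screening visit only.
- **Use.** Protocol 5.2, criterion 4.02, excludes patients with "Impaired prognosis defined as EuroSCORE II > 7% perioperative mortality" at screening. The protocol's rationale for its criteria gives the purpose: "Exclusion criterion 4.02 is to ensure that the perioperative risk of death is compatible with the intended study follow-up duration". Neither document states any other use.
- **Baseline table.** SAP 8.0 lists demographics, body measurements and "other disease characteristics (type of surgery and number of grafts"), plus medical history and medications. EuroSCORE II is not listed.
- **POAF.** SAP 10.1 uses a CMH test stratified by valve surgery (yes/no) and age group (under 65, or 65 and over). SAP 16.0 adds: "Logistic regression models adjusting for baseline risk factors of POAF (type of surgery, and age group) will not be performed".
- **Time to first AF.** SAP 10.2 has a stratified log-rank test and "Cox proportional hazards models adjusting for baseline risk factors of POAF (type of surgery, and age group"), and a further Cox model that also adjusts for total analyzable time.
- **Hospital and ICU stay.** SAP 10.3 has three ANOVAs. The fullest is "An ANOVA model with treatment group, type of surgery, age group, and region as factors". The other two contain treatment with region, or treatment with country, and neither age nor surgery type. Two Van Elteren tests accompany them.
- **Age.** Protocol 5.1 admits ages 55 to 90. The rationale for that criterion says that POAF is more frequent at higher age.

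**The concern.** A prognostic value measured before randomisation can sharpen a treatment comparison or raise its power. Here a candidate value is already scheduled for everyone. The score is not used, and age, which the protocol itself calls prognostic for POAF, is reduced to one cut at 65. Patients aged 65 and 90 fall in the same age group, as do patients with predicted mortality near 0% and at 7% within any stratum.

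Two things are at stake. The first is efficiency, chiefly for hospital and ICU stay. The second is transparency. The score measures perioperative mortality risk, death is the top component of the win ratio in SAP 10.3, and date of death enters the stay derivation. Yet no planned summary shows whether that risk was similar across arms of about 100.

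**Working it through.** **1. Trace the score through the SAP.** It appears in the schedule row and its footnote. It is absent from SAP 8.0, from the CMH strata (10.1), from the AF-burden test, log-rank test and Cox models (10.2), and from the stay analyses and count models (10.3). The factual core holds.

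**2. Reproduce the plan's power figure.** Inputs from SAP 13.0: 47.8% versus 27.8%, 100 per arm, two-sided 0.05.

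- Pooled rate (0.478 + 0.278)/2 = 0.378; null SE = √(2 × 0.378 × 0.622/100) = 0.0686; SE under the alternative = √(0.478 × 0.522/100 + 0.278 × 0.722/100) = 0.0671.
- Without continuity correction: Φ[(0.200 − 1.96 × 0.0686)/0.0671] = 83.6%.
- With continuity correction: Φ[(0.200 − 0.010 − 1.96 × 0.0686)/0.0671] = 79.6%.

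The corrected form matches the stated 80% or so. EuroSCORE II plays no part in it.

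**3. Length of stay (linear model).** Let R² be the share of residual variance that the score explains beyond the factors already in the model. The documents give no value, so R² is an **assumption**, and nil is included. SE factor = √(1 − R²); equivalent sample per arm = 100/(1 − R²); a comparison that would otherwise have 80% power has Φ[(1.960 + 0.842)/√(1 − R²) − 1.960].

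| Assumed R² | SE factor | Equivalent per arm | Power |
|---|---|---|---|
| 0 | 1.000 | 100 | 80.0% |
| 0.01 | 0.995 | 101 | 80.4% |
| 0.05 | 0.975 | 105 | 82.0% |
| 0.10 | 0.949 | 111 | 84.0% |
| 0.20 | 0.894 | 125 | 88.0% |

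Last row: 2.802/0.894 − 1.960 = 1.17, and Φ(1.17) = 88%. The 80% is a reference point; the plan states no power for stay.

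**4. POAF.** A simulation used 6,000 trials per setting and 100 per arm. Marginal rates were held at 47.8% and 27.8%. There were four strata with no effect of their own and a standard normal covariate. The odds ratio per SD is an **assumption**. The planned stratified CMH test was compared with a logistic model containing treatment, strata and the covariate.

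| Assumed OR per SD | CMH power | Logistic power with covariate | Variance of risk difference, adjusted/unadjusted |
|---|---|---|---|
| 1.0 | 83.2% | 83.3% | 1.01 |
| 1.2 | 83.0% | 83.6% | 1.00 |
| 1.5 | 82.5% | 84.2% | 0.97 |
| 2.0 | 82.7% | 86.5% | 0.91 |
| 2.5 | 82.8% | 88.3% | 0.85 |

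The simulation error of each power is about √(0.83 × 0.17/6000) = 0.5 points, so the gain is close to nil up to an odds ratio of about 1.2. These tests carry no continuity correction, so their base is the 83.6% of step 2 and not the stated 80%.

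**5. Time to event.** No figure was computed for the Cox models, and none is claimed.

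**The case against.** The case for leaving the plan alone is respectable. Adjusting for the stratification factors is valid, and both documents name surgery type and age group as the baseline risk factors for POAF. The rationale for criterion 4.02 ties EuroSCORE II to risk of death, not to POAF or stay, and the 7% cut-off narrows its range. Stay already has five comparison methods without multiplicity adjustment. Medical history and prior medications are tabulated by arm, and table specifications sit in a separate document that may already include the score.

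Much of this stands, and it rules out several stronger readings that a reader might infer:

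- **That the plan certainly gives up precision.** This needs an association with outcome beyond the planned factors. The documents give none, so the gain may be nil.
- **That using the score costs nothing.** Neither document says that the numeric score, rather than a yes/no on eligibility, is held in the database. Coding and a missing-value rule would also be needed.
- **That unexplained variation simply sits in the error term of every model.** This describes the linear stay models. In Cox and logistic models a prognostic covariate changes the estimand to a conditional effect and mainly raises power.
- **That SAP 16.0 was wrong to drop the logistic model.** Its reason, that the stratified CMH output already gives adjusted odds ratios, is sound for the model it dropped. A model with the score and continuous age would be a new one.

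What the objection does not show is any bias or loss from using a pre-randomisation value in supportive models. Nor does it answer the point on age, which rests on the protocol's own statement.

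**Conclusion.** This is an optional improvement, not an error, and no stated figure changes. EuroSCORE II is scheduled for all and absent from every baseline summary and model described in the SAP, and age is used only as two groups. Under the assumed ranges, the SE for stay would fall by 0% to 11% (80% power becoming 80% to 88%), and POAF power would move from about 83% to 83%-88%. Where the truth lies in those ranges cannot be told from the documents. Step 3 holds for a linear model with the same R² in each arm. Step 4 holds for strata without an effect of their own and a normally distributed covariate. The calculations concern one added covariate; no separate gain was computed for continuous age. The request to tabulate the score by arm depends on none of these assumptions.

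**What to change.** Specify the following before the interim/primary lock, when SAP 12.0 unblinds sponsor study personnel. Anything added later should be labelled post hoc.

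1. **SAP 8.0:** add EuroSCORE II by arm to the baseline table.
2. **SAP 10.3:** add log EuroSCORE II and continuous age to the stay ANOVA that already has surgery type, age group and region.
3. **SAP 10.2 and 10.1:** add a supportive Cox model and a new supportive logistic model, each with treatment, surgery type, continuous age and log EuroSCORE II. State that they estimate a conditional effect. Keep the stratified CMH test as primary.

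The cost is small but not nil. The sponsor must confirm that the numeric score is in the database, including for anyone screened before Amendment 1 added the schedule row. It must also fix the coding and a simple missing-value rule, and run a few extra models. No new assessment is added to the schedule.
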